7.4.3 Effectiveness Analysis

Effectiveness Analysis will be assessed via the following secondary endpoints:

- Successful clearance of necrosis in the collection being treated during direct endoscopic necrosectomy where success is defined as at least 70% of the necrotic debris in the WOPN cavity is removed based on CT evaluation of the cavity at 21 (+/-7) day follow up visit.
- Assessment of total procedure time to achieve clearance of necrosis for all procedures
- Assessment of adequacy of debridement
- Assessment of total number of procedures to achieve clearance of necrosis
- Assessment of length of hospital stay and utilization
- SF-36 Questionnaire

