4.2 Overview of Study Design

A prospective, single arm, open label, multi-center, trial to evaluate the safety and effectiveness of the Interscope EndoRotor® Resection System in subjects requiring direct endoscopic necrosectomy with walled off pancreatic necrosis (WOPN). Total enrollment of 30 subjects with at least 15 enrolled in the US.

Subjects will be debrided with the EndoRotor at least 2 days following initial stent placement with a maximum of 4 EndoRotor procedures. A minimum of 2 days is required between each EndoRotor procedure and all procedures need to be completed within a 14 (+7/-0) day period. Follow up is completed to 21 (+/-7) days after first EndoRotor debridement procedure.

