5.3.5 Procedural Details

Following placement of EUS guided drainage and determination of the subjects meeting I/E criteria a direct endoscopic necrosectomy procedure can be performed at least 2 days following the EUS guided drainage. During the index procedure the EndoRotor® will be set-up and used to resect all visible and accessible necrotic debris. No resection is performed on the pancreatic wall during this procedure. Multiple procedures can be performed to remove necrotic tissue as required.

Details of the subject's index procedure will be documented in the subject's source medical record and on the appropriate CRF, including:

- Date of Procedure
- Method and Type of Sedation
- Verification of resection results
- Time of endoscope insertion and beginning of EndoRotor use
- An estimate of the percent reduction of the necrosis achieved with the EndoRotor based on endoscopic images
- Time the Procedure was Completed (end of EndoRotor use and time endoscope removed)
- Lot and Serial Number of the EndoRotor® console and catheter
- Any Adverse Events

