5.4 Subject Follow-Up

If at any point during post-procedure subject follow-up, a subject's clinical presentation jeopardizes the safety or welfare of the subject, the Investigator should act in the best interests of the subject, utilizing any and all means judged medically necessary.

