5.4.1 Follow-Up Scenarios

There are several scenarios with respect to each individual subject's timeline relative to the severity and volume of WOPN requiring direct endoscopic necrosectomy.

Scenario 1 – Adequate removal of necrotic debris at index procedure. The subject undergoes a

treatment and returns in 21 (+/-7) days for follow-up.

Scenario 2 – Removal of necrotic debris requiring a maximum of 4 endoscopic debridement procedures. The subject undergoes additional treatment(s) with a minimum of 2 days between treatments over a 14 (+7/-0) day period based on endoscopic verification that less than 70% of the necrotic debris has been removed. The subject returns in 21 (+/-7) days following the last debridement procedure performed.

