5.4.2 Follow-up Visit 21 Days (± 7 days)

All subjects will return to the clinic for the 21 (+/-7) day visit as determined from the last EndoRotor procedure. Results of the following study procedures will be recorded in the subject's source medical record and on the appropriate CRF:

- CT Scan Imaging: Record results and the percent resolution of necrotic debris in the collection being treated
- Surveillance endoscopy (only if clinically required) whereby physician can use local standard of care to continue to treat the patient if required
- Physical Exam
- SF-36 Questionnaire

All subjects will exit from the study after this visit; however, all subjects should be followed according to the Investigator's clinical standard practice guidelines for safety.

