5.5 Post Procedure Imaging

Subjects will receive a contrast enhanced, high resolution vascular CT Scan per standard of care at the 21 (+/-7) day follow up visit. The CT will also be used to measure the effectiveness endpoint to validate disease clearance in the collection being treated.

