10.5 Reporting of Adverse Events

All adverse events, including SAE’s and UADE’s, will be monitored from the time of enrollment through the

study exit. A description of the event, including the start date, resolution date, action taken, and the outcome shall be provided, along with the Investigator's assessment of the relationship between the AE and the study device and procedure.

All AE's should be followed until the event is resolved or judged to be clinically stable. The clinical site should plan to provide additional, relevant AE follow-up information to the Sponsor upon request.

All SAEs, DRSAEs, and UADE's must be reported to the Sponsor and/or CRO and the primary Investigator at the site **within 24 hours** of the Investigator becoming aware of the event. Additionally, the Investigator should notify their IRB, and local/national authorities as required, within their specified timeframes. The Sponsor and CRO will decide whether all of the local Investigators need to be informed immediately, or whether this can be postponed until the next regularly scheduled study update.

A completed SAE CRF **must** be uploaded to the Sponsor's secure web server **within 7 days of the event**. The minimum required data to be recorded for an SAE includes: date of event, type of event, duration of event, severity, seriousness, action taken, outcome, causality and relationship to the Interscope device and procedure. In the case of a DRSAE, whenever possible, the device involved in the failure or malfunction is to be returned to Interscope for analysis.

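### Clearance is judged on the follow-up CT alone, so a subject cleared by other treatment before that CT would, read literally, count as an EndoRotor success

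*Combined protocol and SAP*

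**What the plan says.** - **Endpoint.** Sections 4.4 and 7.4.3 concern clearance of the treated collection during direct endoscopic necrosectomy. The criterion reads: "where success is defined as at least 70% of the necrotic debris in the WOPN cavity is removed based on CT evaluation of the cavity", applied to the visit on day 21 (+/-7). Section 5.5 gives the measurement: "The CT will also be used to measure the effectiveness endpoint to validate disease clearance in the collection being treated".
- **Timing.** "All subjects will return to the clinic for the 21 (+/-7) day visit as determined from the last EndoRotor procedure" (5.4.2). Section 5.4.1 and Appendix 1 (note 4) also count from the last procedure. Section 4.2 counts from the first.
- **Device cap.** Subjects are treated "with a maximum of 4 EndoRotor procedures" (4.2), at least 2 days apart and within 14 (+7/-0) days. A repeat procedure is given "based on endoscopic verification that less than 70% of the necrotic debris has been removed" (5.4.1).
- **Other treatment.** Section 5.4 covers a subject whose state is one that "jeopardizes the safety or welfare of the subject, the Investigator should act in the best interests of the subject, utilizing any and all means", provided the treatment is thought necessary on medical grounds. Section 5.4.2 also permits local standard-of-care treatment at the follow-up visit if clinically required, without saying whether the CT comes first.
- **Records.** The index procedure form includes "An estimate of the percent reduction of the necrosis achieved with the EndoRotor based on endoscopic images" (5.3.5). For adverse events, "A description of the event, including the start date, resolution date, action taken, and the outcome shall be provided" (10.5). Section 5.3.6 tracks the number of procedures, and 5.4.3 records findings at unscheduled visits, including endoscopy.

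**The concern.** The CT shows how much debris is left; it cannot show what removed the rest. A subject can use all four EndoRotor procedures, remain below 70%, have snare work, surgery or added drainage, and then meet the CT criterion. Section 5.4.1 describes adequate removal at the index procedure and removal needing up to four procedures. It does not describe a subject still below 70% after the last one. None of 4.10, 4.14, 7.2, 7.4.3 or 7.5 says how to score that subject.

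There is no control arm, and section 7.4.3 assesses effectiveness only through secondary endpoints, of which clearance is the first listed. Section 7.3 wants the efficacy data to support a benefit/risk evaluation, and 7.1 wants an effect size for powering later studies. A rate that mixes clearance by the device with clearance by rescue is a poor basis for either.

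**Working it through.** The plan states no target rate, power or expected clearance rate, so there is no figure to reproduce. The check is whether the situation can arise, whether any rule covers it, and what one subject is worth.

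**1. Is there time for it to happen?**
- Earliest fourth procedure at 2-day spacing: days 0, 2, 4, 6.
- CT window from the last procedure: 21 - 7 = 14 to 21 + 7 = 28 days.
- With the cap reached, any further debridement before the CT has to be done without the EndoRotor.
- If follow-up were counted from the first procedure, as in 4.2, the CT would fall on days 14 to 28. With a fourth procedure on day 6 the gap is then 14 - 6 = 8 to 28 - 6 = 22 days. The window is shorter but still there.

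**2. Does any rule cover it?**
- 4.14 withdraws subjects whose procedure the investigator terminates and leaves them out of the analysis. That is a different group from subjects who complete the permitted procedures and are treated otherwise later.
- 7.2 defines populations by eligibility, attempted procedure and procedure received. None depends on later treatment.
- 7.5 rules out imputation. A rescued subject with a CT has no missing value, so 7.5 does not apply.
- 5.3.6, 5.4.3 and 10.5 would capture many such treatments, but nothing links those records to the clearance score.

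**3. What is one subject worth?** With N = 30 (7.3), each rescued subject counted as cleared adds 1/30 = 3.3 points. If only 25 subjects had a CT (assumed), it would be 1/25 = 4.0 points.

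**4. Illustration with assumed counts.** Suppose 21 subjects clear with no other treatment and r more are rescued and meet the CT criterion. The overstatement, if none of the r had reached 70% with the EndoRotor, is r/30:

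| r (assumed) | Rescued scored as not cleared | CT alone | Difference |
|---|---|---|---|
| 0 | 21/30 = 70.0% | 21/30 = 70.0% | 0 |
| 1 | 21/30 = 70.0% | 22/30 = 73.3% | 3.3 points |
| 3 | 21/30 = 70.0% | 24/30 = 80.0% | 10.0 points |
| 5 | 21/30 = 70.0% | 26/30 = 86.7% | 16.7 points |

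Exact (Clopper-Pearson) 95% intervals: 21/30, 50.6 to 85.3%; 24/30, 61.4 to 92.3%. Leaving the three rescued subjects out would give a third answer, 21/27 = 77.8%. The plan does not choose among the three.

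**5. The opposite error.** A rescued subject who had already reached 70% with the EndoRotor is a true device clearance. Scoring that subject as not cleared understates the rate by 3.3 points. In the r = 3 case, if one of the three was in this position, the figure would be 22/30 = 73.3%. This is why the fix includes a sensitivity analysis.

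**The case against.** **The definition is narrower than the CT test.** The lead-in ties clearance to direct endoscopic necrosectomy. Section 4.5 uses that term for the EndoRotor procedure, and 4.10 times the CT from the final such procedure where 5.4.2 times it from the last EndoRotor procedure. An EndoRotor-only reading is therefore available. But 1.1 applies the same term to work with snares, forceps and baskets, and the stated test of success is still the CT. The wording allows the narrower reading without setting a scoring rule.

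**The route to rescue is limited.** Section 5.4 is a safety clause and does not provide for routine further debridement. The express provision for continued local treatment (5.4.2) sits at the follow-up visit and is listed after the CT. This stands as a reason to expect few cases.

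**A reader would see the rescues anyway.** Adequacy of debridement and number of procedures are separate endpoints, and many rescues would be reported as serious adverse events. This helps interpretation but does not change how clearance is scored.

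**Stronger readings that the documents do not support.**
- A reader might infer that rescued subjects are definitely scored as successes because the plan is silent. Silence leaves the scoring open. What can be said is that the literal criterion would count them.
- A reader might take 12% of 30 = 3.6 subjects, from the 88% resolution in 1.3, as the expected number of rescues. Those are unresolved patients; one who stays unresolved fails the CT test and causes no bias. Likewise, the earlier series in 1.2 reports complete removal in 12 of 12 patients. The exact upper 95% limit for 0/12 is 26.5%, or 7.9 of 30, but that bounds non-clearance and is not a rescue rate.

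**Conclusion.** The point holds in a limited form. The stated criterion does not attribute clearance to the device, other treatment is allowed before the CT, and no rule says how to score a subject cleared that way. If such subjects occur and the criterion is applied literally, the device clearance rate is overstated by 3.3 points for each one who had not already reached 70% with the EndoRotor. The number of such subjects cannot be derived from the documents and may be zero; the counts in the table are assumptions. At N = 30, a shift of one or two subjects (3.3 or 6.7 points) is well inside the exact interval.

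The severity is minor. The study is mainly a safety evaluation (4.7), clearance is secondary and descriptive, and 7.1 says the endpoints do not define study success. No error rate, sample size or decision rule changes. It is still worth correcting, because the rate is carried into the benefit/risk evaluation and into later planning, and because in an open-label study the scoring is better fixed before results are known.

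**What to change.** 1. In 4.4 and 7.4.3, score as not cleared any subject who, before the follow-up CT, had non-EndoRotor debridement, surgery or added drainage to treat residual necrosis in the treated collection.
2. Report the CT-only rate, by any means, beside it, and list the interventions with date, type and reason.
3. Record the percent estimate in 5.3.5 at every EndoRotor procedure. It is now listed only for the index procedure, although 5.4.1 already calls for an endoscopic judgement against 70% before a repeat. Use it in a sensitivity analysis that counts rescued subjects already at 70% or more with the EndoRotor on their CT result. It belongs there and not in the main rule because it is an unblinded endoscopic estimate.
4. State in 5.4.2 that the follow-up CT precedes any treatment at that visit unless an emergency prevents it.

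**Cost.** One clause in the endpoint definition, a short case report form entry and one table, with no added visits or procedures. Physicians remain free to treat. The reported rate may be slightly lower, and deciding whether an intervention was for residual necrosis needs some investigator judgement.

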7.5 Missing Data

Missing data within this subject cohort is expected to occur at a low rate. All efforts will be made to prevent the occurrence of missing data. Site training and regular monitoring will help to minimize missing data. Due to the sample size and nature of this pilot study, there will be no imputation of missing data. In other words, analyses will be based only on available data.

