4.5 Clinical Sites & Enrollment

Up to six (6) research sites in the United States and up to four (4) research sites in the European Union will participate in this trial. The sites will enroll a total of 30 subjects meeting all inclusion and exclusion criteria to reach a total of 30 evaluable subjects. Once the informed consent process is completed and final study eligibility has been confirmed, the patient will have the EndoRotor direct endoscopic necrosectomy.

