4.9 Subject Screening

Following placement of stent and determination of need for necrosectomy study eligibility is confirmed and the patient will receive the EndoRotor® intervention. The patient will be enrolled upon insertion of the catheter into the endoscope. Screening shall include:

- Pregnancy test – within 1 day of the procedure.
- Medical clearance in advance of the procedure.
- WOPN resulting from necrotizing pancreatitis per high resolution vascular CT with the characteristics per the 2012 Revised Atlanta Classification.
- Imaging suggestive of greater than 30% necrotic material
- WOPN size ≥ 6 cm and ≤ 22 cm

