4.14 Study Withdrawal & Lost to Follow Up

Study participation is voluntary and subjects may withdraw their consent at any time. **ALL** enrolled subjects and their status in the study will be included in the study reports.

- **Treated and Study Criteria Not Met:** Subjects who are enrolled and treated, but who are later discovered to not meet all of the study criteria, will remain in the study and complete all of the study testing and follow-up requirements. A protocol deviation will be completed for study subjects who are

found to be ineligible after enrollment. These subjects may be excluded from the Per Protocol analysis depending upon the nature of the protocol deviation.

- **Patient Withdrawal:** Participation in any clinical investigation is voluntary and a patient is allowed to discontinue their participation at any time. Subjects may withdraw at their own discretion with or without reason and without any impact on their continued medical care. If a patient voluntarily withdraws from the study, no additional medical data will be collected, and the patient will not continue in the study.
- Subjects who withdraw from the study will not be replaced; however, if a patient withdraws their consent **BEFORE** being treated with the study device (before insertion of the catheter into the endoscope), and/or before the 21 (+/-7) day follow-up, he or she will not be included in the analysis.
- **Investigator Termination:** The site Investigator may terminate the patient’s procedure if it is in the patient’s best interest not to continue; however, the patient is withdrawn from the study and will not be included in the analysis.
- **Lost-to-Follow-up:** A patient who does not complete follow-up requirements and does not officially withdraw from the study is considered lost-to-follow-up. This does not apply to missed visits where the patient misses one of the follow-up contact time points but completes the subsequent one. In order to consider a patient lost-to-follow-up, site personnel should make all reasonable efforts to locate and communicate with the patient. All attempts to contact the patient must be recorded in the study notes, including the date, time, and name of site personnel who have attempted to contact the patient.

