5.3.3 Screen Failures

Enrolled subjects failing to meet inclusion / exclusion criteria at the time of index procedure will not be treated with the EndoRotor® device and; therefore, are classified as screen failures. Any baseline study data captured in the CRFs will be collected. Only subjects in whom the EndoRotor® catheter will be followed and study data analyzed.

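### The exclusions in 4.14, available-data analysis in 7.5 and no named population in 7.4.3 can drop plausible failures from the CT clearance denominator, so the rate can be overstated

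*Combined protocol and SAP*

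**What the plan says.** All references are to the combined protocol and SAP.

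- **Endpoint (7.4.3).** Clearance is success if "at least 70% of the necrotic debris in the WOPN cavity is removed based on CT evaluation of the cavity" at the day-21 visit. The section lists the effectiveness endpoints without an analysis population. By contrast, 7.4.2 assigns the safety analysis to the Safety set.
- **Withdrawal (4.14).** A subject who withdraws consent before treatment is left out, but the sentence continues: "and/or before the 21 (+/-7) day follow-up, he or she will not be included in the analysis". This reaches subjects already treated. No further data are collected after voluntary withdrawal, and withdrawn subjects are not replaced.
- **Investigator termination (4.14).** If the investigator ends the procedure in the patient's interest, "the patient is withdrawn from the study and will not be included in the analysis".
- **Missing data (7.5).** "there will be no imputation of missing data. In other words, analyses will be based only on available data". Missing data are expected to be few, and no figure is given.
- **Sample size (4.5).** The plan is to enrol 30 "to reach a total of 30 evaluable subjects", which leaves no allowance for loss.
- **Candidate populations.** Section 7.2 defines a Safety set (procedure attempted) and a Treated set (debridement successfully delivered) but assigns neither to effectiveness. The Protocol Summary has a Primary Analysis entry covering eligible, treated subjects. It is not linked to clearance.
- **Enrolment (4.9).** "The patient will be enrolled upon insertion of the catheter into the endoscope".
- **Reporting (4.14).** All "enrolled subjects and their status in the study will be included in the study reports".

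**The concern.** Subjects leave the clearance denominator by two routes. Section 4.14 removes two kinds of attempted subject by rule. Section 7.5 then removes anyone without a day-21 CT, including subjects who die first, are lost to follow-up or miss the scan.

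These subjects need not resemble those who are scanned. A procedure stopped in the patient's interest is a plausible non-clearance, and so is a death before the CT. Section 5.4.1 sends subjects with less than 70% removal on to further procedures, so slower responders have more occasions to leave. Section 1.2 cites mortality of 15-30% in infected necrosis. That is not a rate for this trial, but it shows that death before the CT cannot be dismissed.

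No hypothesis is tested, so the estimate and its interval are the effectiveness result. Sections 4.7 and 7.3 rest a benefit/risk evaluation on these data, and 7.1 plans to use them for the effect size in later studies. If the rate carried forward leaves out failures, those studies could be planned on too favourable a figure.

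**Working it through.** **Step 1. Does any passage fix the denominator?** Four readings can be set side by side:

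- The 7.2 Safety set keeps withdrawn and terminated subjects once a procedure has been attempted. Section 4.14 removes them.
- The 7.2 Treated set requires successful delivery, so it could drop failed attempts.
- The Protocol Summary's eligible-treated set includes treated subjects whom 4.14 removes, and is not tied to clearance.
- Enrolment at catheter insertion (4.9) makes an attempted subject an enrolled one, yet 4.14 can still leave that subject out of the analysis.

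No passage chooses among these for clearance. None says how a subject without a CT is counted, and no sensitivity analysis is planned.

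**Step 2. How much can it matter?** There is no planned clearance or precision figure to reproduce, because 7.3 states that the sample size is not statistically based.

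Inputs:
- N = 30 (7.3), with no replacement of withdrawn subjects (4.14).
- m = number of attempted subjects without a usable CT. This is assumed to be 1 to 3, since 7.5 says only that the rate is low.
- Three observed non-clearances, also assumed, so x = 30 − m − 3 observed clearances.
- k = number of the m missing subjects who in truth cleared (unknown, 0 to m).

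Formulas:
- available-CT rate = x/(30 − m)
- all-attempted rate = (x + k)/30
- gap = x/(30 − m) − (x + k)/30

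Exact (Clopper-Pearson) 95% intervals are in brackets.

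| m | Available CT | All attempted, all missing failed (k = 0) | Gap, points | All attempted, all missing cleared (k = m) | Gap, points |
|---|---|---|---|---|---|
| 1 | 26/29 = 89.7% (72.6-97.8) | 26/30 = 86.7% (69.3-96.2) | 3.0 | 27/30 = 90.0% (73.5-97.9) | −0.3 |
| 2 | 25/28 = 89.3% (71.8-97.7) | 25/30 = 83.3% (65.3-94.4) | 6.0 | 27/30 = 90.0% (73.5-97.9) | −0.7 |
| 3 | 24/27 = 88.9% (70.8-97.6) | 24/30 = 80.0% (61.4-92.3) | 8.9 | 27/30 = 90.0% (73.5-97.9) | −1.1 |

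For m = 3 the intermediate cases are k = 1, 25/30 = 83.3%, gap 5.6; and k = 2, 26/30 = 86.7%, gap 2.2. The gap is zero when the missing clear at the observed rate, that is k = m·x/(30 − m). For m = 3 this is 3 × 24/27 = 2.67.

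**Step 3. Does the assumed rate drive the result?** At an observed rate near 70%:
- m = 1: 20/29 = 69.0%, against 20/30 = 66.7% to 21/30 = 70.0% (gap 2.3 to −1.0).
- m = 3: 19/27 = 70.4%, against 19/30 = 63.3% to 22/30 = 73.3% (gap 7.0 to −3.0).

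The worst-case gap is somewhat smaller and the range still crosses zero.

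**The case against.** Clearance is secondary, has no test or success threshold, and 4.7 says the endpoints are not powered. Section 7.1 says the endpoints do not define study success. The status of every enrolled subject will be reported, so a careful reader could rebuild a rate out of 30. That the missing subjects are failures is an inference: it is reasonable for stopped procedures and deaths, but nothing in the documents supports it for withdrawn consent or missed scans. One missing subject moves the rate by at most 3.0 points, inside an interval 97.8 − 72.6 = 25.2 points wide. Scoring missing as non-success is itself a choice and biases the rate downward if scans are missing for unrelated reasons.

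All of this limits the weight of the point. It does not remove it. Section 4.14 states an exclusion rule rather than leaving a gap, and reporting status does not settle in advance which rate is the headline.

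Some stronger readings are not supported:

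- **That the rate will be overstated, by up to 8.9 points.** That figure is a worst-case bound on assumed inputs, and the same table reaches −1.1.
- **That losses would be concealed.** Section 4.14 requires status reporting.
- **That 5.3.3 already fixes a catheter-insertion analysis set.** Its sentence ("catheter will be followed and study data analyzed") lacks words before this fragment and is weak evidence either way.
- **That collections cleared by other treatment will be scored as successes.** Section 5.4 is a general safety clause. Section 5.4.2 mentions continued local treatment only at the day-21 visit, and 5.4.3 records unscheduled visits. No rule covers other treatment before the CT, but the documents do not show that it would inflate the rate.

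**Conclusion.** The point holds as a conflict over the denominator. Sections 4.14 and 7.5 together remove attempted subjects from the clearance rate, 7.4.3 names no population, and the sets in 7.2 and the Protocol Summary do not agree with 4.14. The textual finding is firm. That the rate can be overstated follows if those removed clear less often than those scanned, which is plausible but not documented.

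On the assumption of three observed non-clearances, the possible difference runs from 3.0 to −0.3 points with one subject missing and from 8.9 to −1.1 points with three. Since 7.5 expects few missing data, the smaller case may be nearer. No error rate or decision rule is affected. The consequence is for the effectiveness estimate that goes into the benefit/risk evaluation and the planning of later studies, and that is enough to justify a correction this cheap.

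**What to change.** 1. **Amend 4.14** so that only subjects who withdraw before catheter insertion are left out of the analysis. Attempted subjects who later withdraw or are terminated stay in, with data up to that point. Reconcile this with the Primary Analysis entry in the Protocol Summary, the enrolment definition in 4.9 and the populations in 7.2.
2. **In 7.4.3 and 7.5**, name the 7.2 Safety (attempted) set as the clearance denominator. Count death, withdrawal, termination and no evaluable day-21 CT as non-success. Report beside it the available-CT rate and the best- and worst-case rates, each with an exact 95% interval. Show the result in the Protocol Summary's eligible-treated set as a supporting analysis.

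Optional: state how other treatment of the collection before the CT is counted, and summarise number of procedures and total procedure time in all attempted subjects, since 7.4.3 does not say how subjects who never clear enter those two measures.

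The cost is wording in three sections, the reconciliation and some programming. The two main changes add no visits or subjects and alter no clinical rule. The headline rate will be less favourable whenever outcomes are missing, and conservative if scans are missing for unrelated reasons. The available-CT rate beside it shows by how much.
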